#### Exclusion of PK parameters

The ADS ADPP (PK parameters) contains column variables APEXC and APEXCO indicating inclusion/exclusion (APEXC) of a PK parameter and an analysis flag comment (APEXCO). All analyses based on the PKS will include parameters if they are not flagged for exclusion; that is APEXC is equal to "Included".

#### Exclusion of PK concentrations

The ADS ADPC (PK concentrations per time-point or per time-interval) contains column variables ACEXC or ACEXCO indicating inclusion/exclusion (ACEXC) of a concentration and an analysis flag comment (ACEXCO). Exclusion of a concentration depends on the analysis flag comment ACEXCO. For example, if ACEXCO is set to 'ALL CALC', the value will be excluded for all types of analyses based on concentrations. If ACEXCO is set to 'DESC STATS' the value will be excluded from descriptive evaluations per planned time point/time interval. If ACEXCO contains the addition 'TIME VIOLATION' or 'TIME DEVIATION' the value can be used for further analyses based on actual times. If ACEXCO is set to 'HALF LIFE' the value will be excluded from half-life calculation (and, as a consequence, any calculation that relies on  $\lambda_z$ ) only; the value is included for all other analyses.

Further details are given in "Noncompartmental Pharmacokinetic / Pharmacodynamic Analyses of Clinical Studies" [001-MCS-36-472\_RD-01] ([5](#)) and "Description of Analytical Transfer Files and PK/PD Data Files" [001-MCS-36-472\_RD-03] ([7](#)).

## **7.1 DEMOGRAPHIC AND OTHER BASELINE CHARACTERISTICS**

Only descriptive statistics are planned for this section of the report, based on the TS.

SRD part: The data will be summarised by treatment group and in total.

FE part: The data will be summarised by treatment sequence and in total.

## **7.2 CONCOMITANT DISEASES AND MEDICATION**

Frequency tables are planned for this section of the report, based on the TS.

Concomitant diseases will be coded using the coding system of the Medical Dictionary for Drug Regulatory Activities (MedDRA). Medications will be coded using the World Health Organization Drug Dictionary (WHO-DD). The coding version number will be displayed as a footnote in the respective output.

The diagnoses and medications will be listed. Subjects without any concomitant diagnoses or concomitant therapies should be marked with a “No” in the respective column.

The relevance of the concomitant therapies to the evaluation of PK will be decided no later than at the RPM/DBLM.

## **7.3 TREATMENT COMPLIANCE**

**Section 4.3 of the CTP:** *Compliance will be assured by administration of all trial medication in the study centre under supervision of the investigating physician or a designee. The measured plasma concentrations and/or urinary excretion will provide additional confirmation of compliance.*

It is not intended to list the compliance separately. Any deviations from complete intake will be addressed in the RPM/DBLM (cf. TSAP [Section 6.2](#)) and described in the CTR.

## **7.4 PRIMARY ENDPOINT**

Refer to TSAP [Section 7.8](#) for a description of the analysis of safety and tolerability of BI 1358894.

## **7.5 SECONDARY ENDPOINTS**

### **7.5.1 Key secondary endpoint**

This section is not applicable as no key secondary endpoint has been specified in the protocol.

### **7.5.2 Secondary endpoints**

#### Assessment of dose proportionality

Dose proportionality of the PK endpoints  $AUC_{0-\infty}$ ,  $C_{max}$ ,  $AUC_{0-tz}$  in plasma of BI 1358894 will be explored using the power model that describes the functional relationship between dose and PK endpoints. The basic model consists of a regression model applied to log-

transformed data (log-transformation refers to using the natural logarithm). The corresponding ANCOVA (Analysis of Covariance) model includes the logarithm of the dose as a covariate.

The model is described by the following equation:

$$Y_{ij} = \alpha + \beta * X_i + \varepsilon_{ij}$$

where

$Y_{ij}$  logarithm of the pharmacokinetic endpoint for subject  $j$  at dose level  $i$ ;  
where  $i = 1, 2, \dots, n$ ,  $j = 1, 2, \dots, m$ ,

$\alpha$  intercept parameter;

$\beta$  slope parameter;

$X_i$  logarithm of dose  $i$ ;

$\varepsilon_{ij}$  random error associated with subject  $j$  at dose level  $i$  (assumed to be independent and identically normally distributed).

**Section 7.3.2 of the CTP:** *This equation can be fit as a linear regression model.*

*Based on the estimate for slope parameter ( $\beta$ ), a 2-sided 90% CI for the slope will be computed. Perfect dose proportionality would correspond to a slope of 1. The assumption of a linear relationship between the log-transformed pharmacokinetic endpoint and the log-transformed dose will be checked.*

*If dose proportionality over the entire dose range investigated cannot be shown, an attempt will be made to identify dose range(s), where dose proportionality can be assumed.*

*Dose proportionality will be assessed separately for film-coated tablet after fasted (treatment groups of SRD part only) and fed conditions (combination of treatment groups of SRD and FE part).*

This analysis will be accomplished by using the XPKISTAT macro (design DB), based on the PKS.

A regression plot will be performed, where the logarithm of dose is depicted versus logarithm of PK endpoint, including the estimated regression line from the power model and reference line of perfect proportionality ( $\beta=1$ ).

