
* Dose selection based on the assumption to include the potential therapeutic range. In the SRD part doses may be decreased or increased based on the knowledge gained during trial conduct (e.g. safety, exploratory PK analyses). In any case, the selected dose must not exceed the approved dose range. The food effect part will not start before the respective dose has been studied in the SRD part.
 
**The estimated exposure of 200 mg of BI 1358894 administered under fed conditions may exceed the current exposure threshold C_{max} of 980 nM or an AUC_{0-24h} of 9500 nM*h. Since at the time of this 200 mg fed dose group clinical data up to 200 mg fasted and 100 mg fed are available, the exposure threshold for the dose group of 200 mg administered under fed conditions will be further increased to the exposure at NOAEL in rats (i.e. C_{max} of 1960 nM and an AUC_{0-24} of 26300 nM*h). The exposure in previous fed dose groups indicates that the geometric mean of the AUC_{0-24} for the 200mg fed group is predicted to be 15400 nM*h and the geometric mean of C_{max} is predicted to be 1127 nM, i.e. below the new threshold. Even based on the 95% prediction interval the threshold would not be exceeded.
							
mode of admin.: SRD: Oral with 240 mL of water after an overnight fast of at least 10 h FE: Oral with 240 mL of water after an overnight fast of at least 10 h and after a standard high fat breakfast SRD fed: Oral after a standardized high fat breakfast							
Comparator products: Matching placebo tablets dose: Not applicable mode of admin.: SRD: Oral with 240 mL of water after an overnight fast of at least 10 h SRD fed: Oral with 240 mL of water after a standardized high fat breakfast							
Duration of treatment: SRD: 1 single dose FE: 2 single doses [separated by a wash-out period of at least 7 days between drug administrations]							

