- 8 Two identical treatment periods, separated by a wash-out period of at least 7 days between drug administrations; based on sequence intake of study drug under fasted or fed conditions. The duration of wash-out period may be revised based on the PK exploratory analysis in SRD part of the study. Predose at visit 3 Bond & Lader and Bowdle visual analogue scales and suicidality assessment (C-SSRS) will be performed.
- 9 The sample collection schedule may be altered based on the results of PK exploratory analyses in the SRD part
- 10 Treatment allocation only at visit 2

- 12 Based on preliminary PK evaluations, visit days and blood samples may be modified as long as blood loss will not exceed 500 ml
- 13 Time points optional, may be modified after availability of PK data of the SRD part, EOT starts one day after the last ambulatory visit

SRD 200 mg fed Dose group

Visit	Day	Planned time (relative to drug administration [h:min])	Approximate clock time of actual day [h:min]	Event and comment	Safety laboratory	PK blood ⁹	Orthostatic testing	Visual analogue scale ¹²	12-lead ECG	Continuous ECG monitoring	Vital signs (BP, PR, RR)	Questioning for AEs and concomitant therapy ⁶
1	-21 to -1			Screening (SCR) ¹	x		x	x	x		x	
2	-3 to -1	-72:00 ⁷	08:00	Ambulatory visit	x ⁷						x	
	1	-1:30	06:30	Admission to trial site	x ⁵		x				x	
		-0:30	07:30	Allocation to treatment ²	x ¹¹	x ²	x ²		x ²	x ²		
		-0:30	7:30	Standardized breakfast								
		0:00	08:00	Drug administration							▲	
		0:10	08:10			x						
		0:20	08:20			x						
		0:30	08:30			x						
		1:00	09:00			x						
		1:30	09:30			x						
		2:00	10:00	240 mL fluid intake		x						
		2:30	10:30			x						
		3:00	11:00			x						
		4:00	12:00	240 mL fluid intake, thereafter lunch ³	x	x					x x	
		5:00	13:00			x						
		6:00	14:00			x					x x	
		7:00	15:00			x					x x	
		8:00	16:00	Snack (voluntary) ³		x					x x	
		10:00	18:00	Dinner ³		x						
		12:00	20:00			x					x x	
		16:00	24:00			x					x	
	2	24:00	08:00	Breakfast	x	x					x x	
		34:00	18:00			x					x x	
	3	48:00	08:00			x					x x	
	4	72:00	08:00			x					x x	
	5	96:00	08:00			x	x				x x	
	6	120:00	08:00			x					x x	
	7	144:00	08:00	Breakfast, confirmation of fitness ^{13,12} , discharge from trial site		x				x x		
	9	192:00	08:00	Ambulatory visit		x					x x	
	11	240:00	08:00	Ambulatory visit		x					x x	
	15	336:00	08:00	Ambulatory visit		x					x x	
	22	504:00	08:00	Ambulatory visit		x					x x	
	29	672:00	08:00	Ambulatory visit		x					x x	

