5.5 DRUG CONCENTRATION MEASUREMENTS AND PHARMACOKINETICS

Plasma samples will be collected for the purpose of pharmacokinetic analysis

Further information about sampling is provided in [Section 5.5.2](#).

Date and exact clock time of drug administration and pharmacokinetic sampling will be recorded in the CRFs.

PK sampling times and periods may be adapted during the trial based on information obtained during trial conduct (e.g. preliminary PK data), including addition of samples and visits, as long as the total blood volume taken per subject does not exceed 500 mL. Such changes would be implemented via non-substantial CTP Amendments.

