7.3.2 Secondary analyses

The PK parameters (refer to [Section 5.5.1](#)) will be calculated according to the BI Standard Operating Procedure (SOP) ‘Standards and processes for analyses performed within Clinical Pharmacokinetics/Pharmacodynamics’ [[001-MCS-36-472](#)], current version.

Plasma concentration data and parameters of a subject will be included in the statistical pharmacokinetic (PK) analyses if they are not flagged for exclusion due to a protocol violation relevant to the evaluation of PK (to be decided no later than in the Report Planning Meeting) or due to PK non-evaluability (as revealed during data analysis, based on the criteria specified below). Exclusion of a subject’s data will be documented in the CTR.

Relevant protocol violations may be

- Incorrect trial medication taken, i.e. the subject received at least one dose of trial medication the subject was not assigned to
- Incorrect dose of trial medication taken
- Use of restricted medications
- The subject has a protocol deviation relevant to the evaluation of relative bioavailability. (Whether a protocol deviation is relevant, will be decided no later than the Report Planning Meeting.)

Plasma concentrations and/or parameters of a subject will be considered as non-evaluable, if for example

- the subject experienced emesis that occurred at or before two times median t_{max} of the respective treatment (Median t_{max} is to be determined excluding the subjects experiencing emesis),
- missing samples/concentration data at important phases of PK disposition curve.

The PK parameter analysis set (PKS) includes all subjects in the Treated Set (TS) who provide at least one PK parameter that was not excluded according to the description above.

Assessment of dose proportionality

Dose proportionality will be assessed using the pharmacokinetic endpoints as specified in [Section 5.5.1.1](#) (AUC and C_{max}). The specific AUC for the analysis will be defined in the TSAP.

The basic model for the investigation of dose proportionality will be a power model that describes the functional relationship between the dose and PK endpoints.

$$\exp(Y_{ij}) = \alpha' * \exp(X_i)^\beta * \varepsilon'_{ij}$$

Proprietary confidential information © 2018 Boehringer Ingelheim International GmbH or one or more of its affiliated companies

The model consists of a regression model applied to log-transformed data. The corresponding ANCOVA model includes the logarithm of the dose as a covariate.

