Rationale for change	
Oral single doses of up to 25 mg were shown to be well tolerated. There were no SAEs and no AEs considered to be dose limiting. With an oral dose of 25 mg we are approaching the predefined maximum exposure threshold. Since all currently tested dose levels were well tolerated we consider it justified to further increase the exposure threshold which would allow us to test doses beyond 25 mg. We would like to propose an increase of the exposure threshold up to the NOAEL in rats due to the up to now encouraging safety profile in the ongoing Phase I study. We would like to highlight that we continue to stop dose escalation as soon as safety signal as defined in the protocol will be observed.
 
In context with these changes a few remaining inconsistencies were also corrected.

Proprietary confidential information © 2018 Boehringer Ingelheim International GmbH or one or more of its affiliated companies

Number of global amendment	5
Date of CTP revision	06 February 2018
EudraCT number	2017-000143-40
BI Trial number	1402-0001
BI Investigational Product(s)	BI 1358894
Title of protocol	Safety, tolerability and pharmacokinetics of single rising oral doses of BI 1358894 in healthy male subjects (single-blind, partially randomised, placebo-controlled parallel group design) and effect of food on the relative bioavailability of BI 1358894 (open-label, randomised, two-way cross-over)
To be implemented only after approval of the IRB / IEC / Competent Authorities	
To be implemented immediately in order to eliminate hazard – IRB / IEC / Competent Authority to be notified of change with request for approval	
Can be implemented without IRB / IEC / Competent Authority approval as changes involve logistical or administrative aspects only	
Section to be changed	Synopsis and different sections throughout the protocol:
Description of change	Hospitalisation period will be prolonged to 48 h instead of 34 hours.
Rationale for change	Based on interim PK-data of the ongoing study the preliminary half-life was calculated to be in a range of about 40 hours instead of an initially predicted human half-life of about 15 hours. Because of the longer half-life it is considered necessary to extend the observation period to at least 48 hours.

Proprietary confidential information © 2018 Boehringer Ingelheim International GmbH or one or more of its affiliated companies

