#### **5.2.2 Secondary endpoints**

##### **Section 5.5.1.1 of the CTP:**

- *AUC0-tz (area under the concentration-time curve of the analyte in plasma over the time interval from 0 to the last quantifiable data time point  $t_z$ )*
- *AUC0-∞ (area under the concentration-time curve of the analyte in plasma over the time interval from 0 extrapolated to infinity)*
- *Cmax (maximum measured concentration of the analyte in plasma)*

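### Does pooling fed profiles sampled to 192 h with fed profiles sampled to 672 h distort the AUC0-tz dose-proportionality slope?

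*SAP*

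**What the plan says.** SAP 7.5.2 fits a power model (log endpoint on log dose) to AUC0-∞, Cmax and AUC0-tz, with a two-sided 90% CI for the slope. The fasted fit uses the SRD groups only. The fed fit uses "fed conditions (combination of treatment groups of SRD and FE part"): 50 and 100 mg fed from the FE part and 200 mg fed from the SRD part.

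AUC0-tz is the "area under the concentration-time curve of the analyte in plasma over the time interval from 0 to the last quantifiable data time point" (SAP 5.2.2, quoting protocol 5.5.1.1), so its window depends on the sampling schedule and on the assay limit.

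The schedules differ. The FE Flow Chart ends at 192 h, and footnote 13 says of the samples from 72 h onward: "Time points optional, may be modified after availability of PK data of the SRD part". The 200 mg fed Flow Chart continues with samples at 240, 336, 504 and 672 h. The two FE periods are "separated by a wash-out period of at least 7 days between drug administrations" (footnote 8). Protocol 5.5 also lets the schedule grow, "including addition of samples and visits, as long as the total blood volume taken per subject does not exceed 500 mL".

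On the choice of AUC, protocol 7.3.2 says: "The specific AUC for the analysis will be defined in the TSAP". The SAP answers by naming both AUC0-∞ and AUC0-tz.

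**The concern.** Window length is tied to dose. The two lower fed doses stop at 192 h at the latest under the Flow Chart, and only the highest dose can accumulate area after that. Even under exact dose proportionality, AUC0-tz then captures a larger share of total exposure at 200 mg than at 50 or 100 mg, and the fitted slope exceeds 1. The visible SAP text offers no AUC over a common window for this model and does not say which AUC carries the fed conclusion. If the effect were large, a sampling artefact could be read as more than proportional exposure under fed conditions. It could also disturb the planned search for dose ranges in which proportionality holds.

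**Working it through.** The plan gives no expected slope or precision for the fed model, so it has no figure of its own to reproduce.

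**Inputs from the documents**
- Subjects on active drug: 12 at 50 mg fed, 12 at 100 mg fed, 6 at 200 mg fed (SAP 6.1).
- Last scheduled sample: 192 h (FE) and 672 h (200 mg fed).
- Half-life: "the preliminary half-life was calculated to be in a range of about 40 hours" (protocol section 11, rationale of global amendment 5).
- Minimum wash-out: 7 days = 168 h.

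**Assumptions**: exact proportionality, mono-exponential decline, and all samples quantifiable to the end of the schedule unless stated.

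**Step 1, regression weights.** With x = ln(dose), the mean is 4.467 and Sxx = 8.07. The 200 mg group lies ln(200) − 4.467 = 0.832 above the mean. If the log captured fraction is yFE at both FE doses and y200 at the top dose, then

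slope shift = (6 × 0.832 / 8.07) × (y200 − yFE) = 0.618 × (y200 − yFE).

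**Step 2, captured fraction** f(W) = 1 − 2^(−W/t½), at t½ = 40 h.
- f(192) = 0.9641, so 3.6% of AUC0-∞ lies beyond 192 h.
- f(672) = 0.99999.
- Shift = 0.618 × [ln(0.99999) − ln(0.9641)] = **+0.023**.

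If the 200 mg profiles are quantifiable only to 336, 240 or 192 h, the shift is +0.021, +0.013 or 0.

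**Step 3, wash-out and carry-over.** With a 168 h wash-out, a Period 1 sample at 192 h would fall after the second dose, so profiles of fed-first subjects end at 168 h: f(168) = 0.9456. Profiles of fed-second subjects gain residual drug: f(192) + r × [2^(−168/40) − 2^(−360/40)], where r is the fasted/fed AUC ratio (assumed 1 to 0.3). Half of the FE subjects are in each sequence.

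| 200 mg fed quantifiable to | Net shift, r = 1 | Net shift, r = 0.3 |
|---|---|---|
| 672 h | +0.012 | +0.024 |
| 240 h | +0.003 | +0.014 |

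Residual drug at the second dose is 2^(−168/40) = 5.4% of its starting level. The r = 1 case therefore sits near the limit in protocol 7.3.5, which drops subjects whose predose value exceeds 5% of Cmax.

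**Step 4, comparison with the precision.** Half-width of the 90% CI = t(0.95; 28) × √ln(1 + gCV²) / √Sxx, with t = 1.701 and √8.07 = 2.841.
- gCV 30%: 1.701 × 0.2936 / 2.841 = 0.176.
- gCV 40%: 0.231.
- gCV 50%: 0.283.

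The gCVs are assumed. The gross shift is 0.023/0.283 to 0.023/0.176, about 8 to 13% of the half-width.

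**Step 5, what would make it material.**
- Longer half-life (200 mg quantifiable to 672 h, FE as in step 3): +0.05 at about 52 to 64 h, +0.10 at about 71 to 90 h.
- Earlier end of FE sampling at 40 h (gross): 168 h +0.035; 144 h +0.053; 96 h +0.130.

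**The case for a change.** The case for acting is that the reassurance rests on a preliminary half-life. The 40 h figure dates from February 2018, before the FE groups and the 200 mg fed group, and no fed half-life is reported. The 672 h schedule spans 672/40 = 16.8 such half-lives, so the 40 h value may not be settled. The FE samples that keep the effect small are the optional ones. The protocol synopsis makes AUC0-∞ conditional on being evaluable, and a partial AUC over a common window costs one derived parameter and two sentences.

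Part of this stands. The windows differ, the FE tail is optional, and the effect would approach the CI half-width if FE sampling had stopped at 96 h. But the documents report neither early stopping nor a longer fed half-life, and protocol 5.5 equally allows samples to be added. The long 200 mg schedule need not mean long quantifiable profiles. The 200 mg fed geometric mean Cmax "is predicted to be 1127 nM, i.e. below the new threshold". Scaled from that value at 40 h, concentrations are about 3.3 nM at 336 h and 0.01 nM at 672 h.

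The remedy also adds little. To 192 h a partial AUC holds 96% of AUC0-∞, so it nearly duplicates an endpoint already in the model. Under the minimum wash-out the common window shrinks to 144 h, because 168 h is not scheduled at 200 mg fed. If FE sampling had ended at 96 h, it would hold only 81%. It corrects neither truncation at the assay limit nor carry-over. Finally, SAP Table 6.3:1 refers to further PK endpoints, so a fixed-window AUC may already be defined in text that is not public.

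**Conclusion.** The mismatch is real but no change to the plan follows, because a change would gain nothing. At about 40 h the fed AUC0-tz slope is shifted by +0.023, or +0.012 to +0.024 with the 7-day wash-out taken into account, against an assumed CI half-width of 0.18 to 0.28. Protocol 7.2 treats the interval as exploratory and sets no acceptance range, so no stated decision depends on a shift of this size. AUC0-∞ goes through the same model on the same subjects, Cmax is unaffected, and SAP 7.5.2 already checks log-linearity and allows restricted dose ranges.

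This rests on linear single-phase decline, a fed half-life near 40 h and FE sampling realised to about 168 to 192 h. The analyst will know the actual sampling times and the half-life when interpreting the fit. The sensible reading is to rely on AUC0-∞ where it is evaluable and to view the fed AUC0-tz slope in the light of the differing windows. Should the fed half-life prove clearly longer, or FE sampling have ended by about 144 h, a partial AUC to the last time sampled in all three fed groups could be added at reporting.

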#### Investigation of relative bioavailability (food effect evaluation – FE part)

**Section 7.3.2 of the CTP:** *Relative bioavailability is primarily to be determined on the basis of the parameters AUC (AUC0-∞, AUC0-tz) and Cmax [...] for the dose levels [...] 50mg, 100mg. [...] Those parameters will be ln-transformed (natural logarithm) prior to fitting the model.*

*The statistical model used for the analysis of AUC0-∞, AUC0-tz and Cmax will be an ANOVA (analysis of variance) model on the logarithmic scale. [...] This model will include effects accounting for the following sources of variation: 'sequence', 'subjects within sequences',*

'period' and 'treatment'. The effect 'subjects within sequences' will be considered as random, whereas the other effects will be considered as fixed. For tests on subject, period, and treatment effects, the denominator sum of squares will be the sum of squares for error; while for tests on sequence effects, the denominator will be the sum of squares for subjects. The model is described by the following equation

$$y_{ijkm} = \mu + \zeta_i + s_{im} + \pi_j + \tau_k + e_{ijkm}, \text{ where}$$

$y_{ijkm}$  = logarithm of response measured on subject  $m$  in sequence  $i$  receiving treatment  $k$  in period  $j$ ,

$\mu$  the overall mean,

$\zeta_i$  the  $i^{th}$  sequence effect,  $i = 1, 2$

$s_{im}$  the effect associated with the  $m^{th}$  subject in the  $i^{th}$  sequence,  $m = 1, 2, \dots, p_i$ ;  
 $p_i$ =number of subjects in  $i^{th}$  sequence

$\pi_j$  the  $j^{th}$  period effect,  $j = 1, 2$

$\tau_k$  the  $k^{th}$  treatment effect,  $k = 1, 2$

$e_{ijkm}$  the random error associated with the  $m^{th}$  subject in sequence  $i$  who received treatment  $k$  in period  $j$ .

The difference between the expected means for test treatments (tablets under fed conditions T1) and reference treatment (tablets under fasted conditions R)  $\log(T1)-\log(R)$ , will be estimated by the difference in the corresponding Least Square Means (point estimate) and two-sided 90% confidence intervals based on the t-distribution will be computed. These quantities will then be back-transformed to the original scale to give the point estimator (geometric mean) and interval estimates for the ratio between response under test and response under reference.

The analysis will be accomplished by using the XPKISTAT macro, based on PKS (design BWC).

In addition, a sensitivity analysis will be performed by fitting the model described above, but using all effects as fixed. This analysis will be done using PROC GLM.

